8.4 COVID-19 Surveillance (All Subjects)

If a subject experiences any of the following (irrespective of perceived etiology or clinical significance), he or she is instructed to contact the site immediately. During the 7 days following each vaccination, potential COVID-19 symptoms that overlap with solicited systemic events (i.e. fever, chills, new or increased muscle pain, diarrhea, vomiting) should not trigger a potential COVID-19 illness visit unless, in the investigator's opinion, the event is more indicative of a possible COVID-19 illness than vaccine reactogenicity.

8.4.1 Taiwan CDC Criteria for Case Definition of COVID-19

[figure not shown]
Criteria	Definition
Clinical Criteria Presentation	One or more of the following: 
 (1) Fever (≥ 38 °C) or symptoms of acute respiratory tract infection. (2) Abnormal sense of smell (anosmia), abnormal sense of taste (dysgeusia), or diarrhea of unknown etiology. (3) .Community-acquired pneumonia (CAP) highly suspected to be COVID-19 by doctors
Laboratory Criteria Diagnosis	One or more of the following: 
 (1) Pathogen (SARS-CoV-2) isolated and identified from a clinical specimen (nasopharyngeal swab, throat swab,

	
expectorated sputum, or lower respiratory tract aspirates).
 
(2) Positive molecular biological testing for viral (SARS-CoV-2) RNA from a clinical specimen (nasopharyngeal swab, throat swab, expectorated sputum, or lower respiratory tract aspirates).

Epidemiological Criteria	
One or more of the following within 14 days prior to symptom onset:
 
(1) History of traveling or living abroad, or contact with symptomatic (fever or other respiratory tract infection symptoms) individuals returning from abroad.
 
(2) History of close contact with symptomatic suspected or confirmed case(s), including caring for or interacting with these individuals, or direct contact with body fluid or respiratory secretions without adequate personal protective equipment (PPE).
 
(3) History of cluster related to confirmed cases.

Reporting Requirements for COVID—19	
Any cases with one or more of the following conditions should be reported to the Taiwan Centers for Disease Control (Taiwan CDC):
 
(1) Meet clinical presentation criteria (1) AND one or more epidemiological criteria.
 
(2) Meet clinical presentation criteria (2) AND any of epidemiological criteria (1) or (2).
 
(3) Meet clinical presentation criteria (3).
 
(4) Meet laboratory diagnosis criteria.

Case Definition	
(1) Suspected case: meet clinical presentation criteria but not laboratory proven, plus history of close contact with symptomatic confirmed case(s) within 14 days prior to symptom onset.
 
(2) Confirmed case: meet laboratory diagnosis criteria, regardless. of clinical signs and symptoms.

8.4.2 Intercurrent COVID-19

If, at any time, a subject develops acute respiratory illness, for the purposes of the study she will be considered to potentially have COVID-19 illness. **In this circumstance, the subject should contact the site, an in-person or telemedicine contact should occur, and assessments should be conducted, as appropriate.** The assessments will include a clinical specimen defined above, which will be tested at a laboratory using an TFDA-approved polymerase chain reaction (PCR) test to detect SARS-CoV-2.

Taiwan CDC Criteria for case definition of COVID-19 is described in Section 8.4.1, and subjects who fulfill the reporting criteria should report to CDC. The diagram for COVID-19 surveillance is as below:

8.4.3 Potential COVID-19 Infection

Through ePRO system, the potential COVID-19 infection will be monitored. Once the events occur, the system alert will be sent to notice the study team members. The in-person or telemedicine contact will be conducted, optimally within 3 days after onset of illness. Several contacts may be required to obtain the following information:

- Record potential COVID-19 illnesses, as appropriate. Note: Potential COVID-19 illnesses that are consistent with the clinical endpoint definition will be recorded on a COVID-19 CRF and will not be listed as AEs.
- Record the results of COVID-19 testing by an authorities approved test, if available
- Schedule an appointment for the subject to return for the potential COVID-19 convalescent visit once he or she has recovered.
- The investigator or designee completes the CRFs on COVID-19 page.

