First interim analysis and report will be performed when all adult immunogenicity data (350 evaluable young adults and 154 evaluable elderly subjects) for Day 57 are available

Second interim analysis and report, as EUA application dossier, will be performed when at least half of core group subjects (at least 3500 evaluable subjects) will be completed Day 85 safety follow up.

Third interim analysis and report, as EUA application dossier, will be performed when all immunogenicity data for lot-to lot consistency of Day 57 are available

Fourth interim analysis and report, as supplementary dossier for EUA, will be performed when 350 evaluable adolescents completed Day 57 safety follow up.

Fifth interim analysis will be performed for immunogenicity and safety data for young and elderly adult subjects receiving 3rd vaccination completed Visit 7, which is 14 days after 3rd vaccination.

Sixth interim analysis will be performed for immunogenicity and safety data for adolescent subjects receiving 3rd vaccination completed Visit 7, which is 14 days after 3rd vaccination.

Planned IDMC Meeting:

1st time: when all adult immunogenicity data (350 evaluable young adults and 154 evaluable elderly subjects) for Day 57 are available

2nd time: when at least half of core group subjects (at least 3500 evaluable subjects) will be completed Day 85 safety follow up. Adolescence could be enrolled after 2nd IDMC meeting.

3rd time: when all immunogenicity data for lot-to lot consistency of Day 57 are available.

4th time: when 350 evaluable adolescents will be completed Day 57 safety follow up.

The meeting schedule might be adjusted based on the progress of recruitment. The independent data monitoring committee (IDMC), consisting of at least two physicians and one statistician, will review the interim analysis results or reports.

Disease-Related Events and/or Disease-Related Outcomes Not Qualifying as AEs or SAEs:

Potential COVID-19 illnesses and their sequelae that are consistent with the disease definition should not be recorded as AEs. These data will be captured as efficacy assessment data only on the relevant pages of the CRF, as these will be expected exploratory endpoints.

Schedule of Assessments**Lot-to-lot consistency & Immunogenicity group**

Scheduled visit	1^m	2^m	3	4	5/ET	6^t	7	Long-term follow-up					

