6.2 Primary Endpoint(s)

Immunogenicity Endpoint(s)

- Geometric mean titer (GMT) of SARS-CoV-2 neutralizing antibody on Day 57
- Seroconversion rate (SCR) of SARS-CoV-2 neutralizing antibody on Day 57

Safety Endpoint(s)

- Local reactions for up to 7 days following each dose
- Systemic events for up to 7 days following each dose
- Unsolicited AEs from Day 1 to Day 57
- MAAEs and SAEs from Day 1 to Day 365
- AESIs and ADEs from Day 1 to Day 365

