8.3 Unscheduled Visit

Subjects who suffer from Grade 3/4 solicited AE should return to site ASAP for further survey and treatment. All AEs recognised during the unscheduled visits are medically attended adverse events (MAAE), except for confirmed COVID-19 disease.

- If a Grade 3 local reaction, systemic event, or fever is reported in the reactogenicity e-diary, a telephone contact should occur to ascertain further details and determine whether a site visit is clinically indicated.
- If suspected Grade 4 local reaction systemic event or fever is reported in the reactogenicity e-diary, a site visit should occur to confirm whether the event meets the criteria for Grade 4.

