8.4.4 COVID-19 Convalescent Visit

This visit may be conducted 28 to 35 days after the Potential COVID-19 Illness Visit.

- Record AEs, as appropriate.

Note: Potential COVID-19 illnesses that are consistent with the clinical endpoint definition should not be recorded as AEs. These data will be captured as efficacy assessment data only on the relevant pages of the CRF, as these are expected endpoints.

- Record details of any of the prohibited medications specified in Section 7.5.4.1 received by the subject if required for his or her clinical care.

- **Collect blood samples for immunogenicity testing:**

- **UBI SARS-CoV-2 ELISA, IgG S1-RBD ELISA, ACE2 binding inhibition ELISA and neutralization tests (~20 mL)**

- Collect/update COVID-19–related clinical and laboratory information
- Complete the source documents
- The investigator or an authorized designee completes the CRFs on COVID-19 page.

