All suspected unexpected serious adverse reactions (SUSARs) will be the subject of expedited reporting. The sponsor and/or the appointed representative(s) shall ensure that all relevant information about a SUSAR that is fatal or life-threatening is reported to the relevant competent authorities and IEC/IRB within 7 days after knowledge by the sponsor of such a case and that relevant follow-up information is communicated within an additional 8 days. All other SUSARs will be reported to the relevant competent authorities and IEC/IRB within 15 days after knowledge by the sponsor of such a case. All investigators should follow up SUSARs until the event is resolved or until, in the opinion of the investigator, the event is stabilized or determined to be chronic. Poststudy SUSARs that occur after the subject has completed the clinical study must be reported by the investigator to the sponsor.

Documentation and Reporting of SARS-CoV-2 infection

All subjects will be surveilled for potential COVID-19 illness from Visit 1 onwards. Potential COVID-19 illnesses and their sequelae that are consistent with the clinical endpoint definition should not be recorded as AEs or SAEs, even though the event may meet the definition of an SAE. These data will be captured as efficacy assessment data only on the relevant pages of the CRF, as these are expected endpoints.

Potential COVID-19 illness events and their sequelae will be reviewed by IDMC. Any SAE that is determined by the IDMC not to meet endpoint criteria is reported back to the SAE reporting process. The investigator's SAE awareness date is the date on which events is confirmed not to meet endpoint criteria.

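### V-205 does not define which potential COVID-19 illnesses are exempt from AE recording, so non-serious unconfirmed illnesses may be counted in neither the COVID-19 endpoint nor the primary safety endpoints

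*Supplement*

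**What the plan says.** All references are to protocol V-205.

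- **Trigger (8.4.2).** When a subject develops an acute respiratory illness, "for the purposes of the study she will be considered to potentially have COVID-19 illness". This applies before any test result.
- **Exemption (8.4.3).** Potential COVID-19 illnesses that match a clinical endpoint definition "will be recorded on a COVID-19 CRF and will not be listed as AEs".
- **Exemption repeated.** Section 8.4.4 applies the same rule at the convalescent visit and adds: "These data will be captured as efficacy assessment data only on the relevant pages of the CRF, as these are expected endpoints". Section 9.5.6.8 extends it to events that would otherwise be SAEs. The synopsis uses a different term: "Potential COVID-19 illnesses and their sequelae that are consistent with the disease definition should not be recorded as AEs".
- **Way back (9.5.6.8).** "Any SAE that is determined by the IDMC not to meet endpoint criteria is reported back to the SAE reporting process". Nothing comparable is written for non-serious events.
- **MAAE rule (8.3).** "All AEs recognised during the unscheduled visits are medically attended adverse events (MAAE), except for confirmed COVID-19 disease".
- **Endpoints.** Section 6.2 makes "Unsolicited AEs from Day 1 to Day 57" a primary safety endpoint, alongside MAAEs and SAEs to Day 365. The COVID-19 incidence endpoint in 6.6 is exploratory and rests on PCR. Section 10.5 draws the unsolicited-AE analysis from the AE eCRF.

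**The concern.** The exemption turns on a term that the visible text never defines, and two different terms are used for it. The rule is attached to potential illness, whereas 8.3 speaks of confirmed disease. If a site takes the term in a clinical sense, a non-serious cold or fever with a negative or absent PCR result goes on the COVID-19 page. It is then not a COVID-19 case, because incidence needs PCR, and it is not in the AE eCRF that 10.5 analyses.

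At stake are two primary safety endpoints, which 10.5.1 compares between arms by Fisher's exact test. Unsolicited AEs also enter the interim reports that 10.9 intends for the EUA dossier. The affected events would be mainly respiratory and febrile illnesses outside the seven days after each vaccination, because 8.4 holds back the illness-visit trigger for overlapping diary symptoms in that period. Two sites could record the same illness in opposite ways and each point to a section that supports it. The analyst could not repair this later from the AE eCRF alone.

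**Working it through.** The plan states no figure on this point, so the check sets the rules side by side.

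**Step 1: candidate meanings of the undefined term.**
- *PCR-confirmed disease*, by analogy with the PCR-based endpoint in 6.6 and with 8.3.
- *The Case Definition row of 8.4.1*. A confirmed case needs laboratory proof. A suspected case meets the clinical criteria without laboratory proof and also had close contact with a symptomatic confirmed case in the preceding 14 days.
- *The clinical criteria of 8.4.1 alone*. Fever of at least 38 °C or acute respiratory symptoms would be enough.

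**Step 2: where a non-serious illness that meets the clinical criteria ends up.**

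| Illness | PCR-confirmed reading | 8.4.1 case-definition reading | Purely clinical reading |
|---|---|---|---|
| PCR-positive | COVID-19 page, counted as COVID-19 | COVID-19 page, counted as COVID-19 | COVID-19 page, counted as COVID-19 |
| PCR-negative or untested, with qualifying close contact | AE eCRF | COVID-19 page, in neither endpoint | COVID-19 page, in neither endpoint |
| PCR-negative or untested, no such contact | AE eCRF | AE eCRF | COVID-19 page, in neither endpoint |

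**Step 3: size.** Let n be the number of non-serious, unconfirmed illnesses meeting the clinical criteria, and c the share of them with qualifying close contact. The number missing from both endpoints is n × f, where f = 0 on the first reading, f = c on the second and f = 1 on the third. The documents give neither n nor c, so only the range of f, from 0 to 1, can be stated. If the same share f is lost in both arms, an arm difference d in the rate of these illnesses appears in the AE tables as (1 − f) × d. That is d unchanged on the first reading and zero on the third.

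**Step 4: can an illness be untested?** Section 8.4.2 includes a PCR specimen in the assessments, but as appropriate. Section 8.4.3 asks for test results if available, and 9.5.7.1 says swabs may be collected. An untested illness is therefore possible.

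**Step 5: MAAEs.** Section 9.5.6.4 defines an MAAE as an AE with a medically attended visit. Under 8.3 an attended, unconfirmed illness is an MAAE. On the third reading of 8.4.3, and for suspected cases on the second, the same illness is not an AE and so cannot be an MAAE. On those readings the sections conflict; only on the first do they agree.

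**The case against.** The strongest defence is that the exemption is conditional. It removes illnesses that match an endpoint definition, the reason given is that these are expected endpoints, and the only COVID-19 incidence endpoint is PCR-based. On that view a PCR-negative cold fails the condition and stays an AE. Other text agrees: 8.3 excepts only confirmed disease, the footnote to Table 9-5 requires a positive PCR for COVID-19 AESIs, 9.5.5.2 and 9.5.5.3 call for collection of unsolicited and all AEs, and 8.4.4 still tells sites to record AEs where appropriate. The sentence on returning SAEs sets a reporting clock that non-serious events do not have, so its silence does not bar them from the AE page. The surveillance diagram announced in 8.4.2 is not shown and may carry a branch for negative tests.

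Much of this stands, and it rules out stronger readings. A reader might infer that V-205 plainly removes all PCR-negative illness on clinical grounds. The text does not establish that, and on the case-definition reading an ordinary cold without close contact stays an AE. A reader might also multiply an assumed illness rate by the 3850 core-group adults and report that many events as missing. The documents give no rate, and the product would assume total loss. Nor can it be said that a vaccine-arm excess would be invisible: illnesses on the COVID-19 page remain in the database, and 9.5.6.8 has the IDMC review potential COVID-19 events.

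The defence does not settle the rule, however. The return clause in 9.5.6.8 presupposes events already held off the SAE record that later fail the endpoint criteria. If only PCR-confirmed disease were held off, the clause would have little to do. The exemption also says potential where 8.3 says confirmed, and still says so at a convalescent visit 28 to 35 days after the illness visit.

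**Conclusion.** The point holds as an undefined exemption with conflicting recording rules, not as a demonstrated understatement of the safety endpoints. The loss of non-serious, PCR-negative or untested illnesses from both the COVID-19 endpoint and the AE eCRF is none on a PCR-confirmed reading, limited to suspected cases with close contact on the 8.4.1 case-definition reading, and complete on a purely clinical reading. No count can be attached.

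This is more than a missing detail. Even the intermediate reading, which fits the synopsis's term, leaves some illnesses in neither endpoint, and it concerns what sites enter on which CRF page, which an analysis plan cannot correct afterwards. The conclusion rests on the visible text; a surveillance diagram that routes unconfirmed illnesses to the AE page would narrow it, but the written sections would still need to agree.

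**What to change.** Reconcile 8.3, 8.4.3, 8.4.4, 9.5.6.8 and the synopsis so that one rule applies: only laboratory-confirmed COVID-19 is exempt from AE recording, as 8.3 already provides for MAAEs. Replace the two undefined terms with that wording. Require any potential COVID-19 illness that is not laboratory-confirmed, whether PCR-negative or untested, serious or not, to be entered in the AE eCRF with its original onset date and grade, and as an MAAE when medically attended.

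The cost is a short text change in each place, a CRF rule that carries unconfirmed illnesses from the COVID-19 page to the AE page, and slightly higher reported AE and MAAE rates.

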8.4.4 COVID-19 Convalescent Visit

This visit may be conducted 28 to 35 days after the Potential COVID-19 Illness Visit.

- Record AEs, as appropriate.

Note: Potential COVID-19 illnesses that are consistent with the clinical endpoint definition should not be recorded as AEs. These data will be captured as efficacy assessment data only on the relevant pages of the CRF, as these are expected endpoints.

- Record details of any of the prohibited medications specified in Section 7.5.4.1 received by the subject if required for his or her clinical care.

- **Collect blood samples for immunogenicity testing:**

- **UBI SARS-CoV-2 ELISA, IgG S1-RBD ELISA, ACE2 binding inhibition ELISA and neutralization tests (~20 mL)**

- Collect/update COVID-19–related clinical and laboratory information
- Complete the source documents
- The investigator or an authorized designee completes the CRFs on COVID-19 page.

8.5 Duration of Treatment

The duration of each visit is expected to last between 2 to 3 hours, barring any unexpected adverse reactions.

It takes about 13 months for each subject to participate in the study, from recruiting to the last visit. Some subjects may withdraw the study during the course of the study.

9 IMMUNOGENICITY AND SAFETY VARIABLES

The planned schedule of assessments is in Section 7.2.

9.1 Informed Consent Form

The investigator or designee must explain to each subject the nature of the study, its purpose, the procedures involved, the expected duration, the potential risks and benefits involved and any potential adverse events. Each subject will be informed that participation in the study is voluntary and that they can be withdrawn from participation at any time.

All subjects must provide a signed and dated informed consent at Visit 1. An informed consent form must be approved by the Institutional Review Board (IRB), Ethics Committee (EC), and/or the applicable health authorities.

9.2 Demographics / Other Baseline Characteristics

The demographic and baseline characteristic data for subjects will be collected at Visit 1. The demographics include date of birth, age, sex and ethnicity. Relevant history/conditions include all those present prior to the administration of study vaccine that are listed below:

- Relevant medical history,
- All current medical conditions,
- Allergy history,

Whenever possible, diagnoses but not symptoms should be recorded.

9.3 Eligibility

Eligibility should be checked by the investigator at Visit 1 and rechecked at Visit 2 before vaccination, these 2 visits could be emerged as one. **For subjects agreed to receive 3rd vaccination, eligibility should be rechecked at Visit 6.**

9.4 Administration

The unblinded staff takes a vial of investigational vaccine/placebo, use a disposable syringe to extract vaccine/placebo and intramuscularly inject it into the middle of the lateral deltoid muscle of the subject's upper arm.

Vaccine administration will be recorded. The containers from which the vaccine is administered to the subjects will be retained for confirmation.

9.5 Safety and Immunogenicity Measurements Assessed

9.5.1 Safety Variables

9.5.1.1 Physical Examination

Complete physical examinations should be conducted by investigator/site staff at all visits. A complete physical exam will include the examination of general appearance, HEENT (head, ears, eyes, nose, throat), neck (including thyroid), lymph nodes, skin, cardiovascular, pulmonary, abdomen, neurological system and musculoskeletal/joints.

Body weight and height will be collected at Visit 1. Body weight will be measured in indoor clothing, but without shoes and blanket to the nearest 0.1 kilogram (kg). Body height will be measured in centimeters (cm).

It must be recorded when any abnormality has been found out.

9.5.1.2 Vital Sign

Systolic/diastolic blood pressure, pulse, respiratory rate, and ear temperature will be collected at all visits.

For two vaccination visits, vital sign should be measured prior to and after vaccine administration. All subjects in each group will be closely monitored by the study staff at pre-vaccination and 30 minutes after vaccination (at least) and the results will be recorded in CRF.

9.5.2 Electrocardiogram(ECG)

A 12-lead electrocardiogram (ECG) will be performed by the investigator or a suitable qualified designee after measurement of vital signs. The ECG measurement should be obtained after the subject has been seated and at rest for at least 5 minutes. The ECGs will be performed at screening visit.

Qualified physicians will interpret the ECG. Any abnormal ECG reading should be noted and recorded in the CRF.

9.5.3 Clinical Laboratory Evaluation

The clinical laboratory analyses will be performed at central laboratory designated by sponsor. Reference ranges will be supplied by the central laboratory and used by the investigator to assess the laboratory data for clinical significance and pathological changes.

Methods and timing for assessing, recording and analyzing each laboratory variable should follow local guidelines. The following laboratory safety tests will be performed:

Blood Routine

CBC, including Hgb, Hct, RBC, WBC with differential, platelet count.

Biochemistry

Creatinine, ALT, AST, total and direct bilirubin; high sensitivity (hs) CRP,

Immunology

Anti-nuclear antibody (ANA)

Urinalysis

Color, **pH**, specific gravity, appearance, nitrate, blood, glucose, ketones, protein, leukocyte esterase, WBC, RBC, casts, epithelial cells, yeast, bacteria

Proteinuria will be checked via urine routine as baseline on Visit 1. **If subject encountered \geq Grade 3 hypertension, the existence or deterioration of proteinuria or other renal damage sign will be checked.**

